5.6.2 Lymphocyte subsets

A sub-study assessing lymphocyte subsets will be conducted in approximately 200 subjects. Participation in the sub-study will be mandatory for all subjects until at least the first 200 subjects are randomized to the main study. T cell, B cell, and NK cell counts as well as T cell subsets (e.g., CD4⁺ naïve, CD4⁺ effector memory, CD4⁺ central memory, CD8⁺ naïve, CD8⁺ effector memory, CD8⁺ central memory, CD8⁺ terminally differentiated effector memory, Th17 cells, Treg cells, and Th1 cells) will be analyzed at the central laboratory. All subjects were to be analyzed for T cell subsets. In addition, the approximately 50 subjects were to be analyzed for B cell subsets. Other lymphocyte subsets may also be analyzed. Selected lymphocyte subsets may also be analyzed functionally *ex vivo*.

Blood samples for lymphocyte subset analysis will be taken from approximately 200 subjects at Visit 2 (Baseline), Visit 6 (Week 12), Visit 7 (Week 24), Visit 9 (Week 48), Visit 13 (Week 96), Visit 17 (Week 144), Visit 18 (EOT), Visit 19 (FU7d), and at Visit 20 (FU). If applicable, lymphocyte subsets will also be assessed at the corresponding visits in the PTOP (Visits 6A, 7A, 9A, 13A, 17A, and 18A).

Absolute and change from baseline values for lymphocyte subsets are derived as described in Section 5.5.12.

6 DEFINITION OF PROTOCOL DEVIATIONS

This section refers to all protocol deviations as recorded in the database following the specifications provided in the protocol deviation code list.

Protocol deviations are categorized while being entered into the database into the following categories:

- **Important** protocol deviations (Yes/No)
- **Timing** (before Randomization / after Randomization / after end of treatment/ anytime during the study)

In addition, protocol deviations are categorized by high-level topic in line with the Protocol Deviation code list [see Appendix B].

7 ANALYSIS SETS

7.1 Definitions of analysis sets

7.1.1 Screened analysis set

The Screened Analysis Set (SCR) includes all subjects who were screened and received a subject number.

7.1.2 Full analysis set

The full analysis set (FAS) includes all randomized subjects who were treated with at least one dose of study treatment and have at least one post-baseline efficacy assessment.

- In order to preserve the randomization, subjects will be evaluated according to the treatment they have been randomized to (which may be different to the treatment they have received) and stratum information used for randomization as recorded in the IVRS system (which may be different to the information available on the eCRF after data validation);
- Unless otherwise stated, all available efficacy data for the primary and secondary endpoints up to the EOS visit [see Section 11.4] will be included in the analysis, regardless of study treatment discontinuation and/or switches to alternative MS treatments.

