5.1.6 Subject study completion status

A subject is considered to have completed the study up to study termination if the corresponding entry on the ‘Study Discontinuation’ eCRF for question ‘Study stopped due to’ is answered with ‘Sponsor decision’ and corresponding specify field is answered with ‘Study termination’. These subjects are considered to have completed study up to study termination.

All subjects not completing the study up to the early termination of the study as defined above are considered to have prematurely discontinued the study.

The EOS date is defined as the ‘Date of Subject Decision’ (if reason for study discontinuation was ‘Subject Decision/Withdrawal of consent’), ‘Date of Physician Decision’ (if reason for study discontinuation was ‘Physician Decision’) collected on the ‘Study Discontinuation’ eCRF, or ‘Date of recorded last study visit / assessment’ (if reason for study discontinuation was ‘Sponsor Decision’), unless a subject is lost to follow-up or dies, in which case ‘Date of last successful contact’ from the Study Discontinuation eCRF or ‘Date of Death’ from Death eCRF are used. If missing, the last recorded visit date (i.e., the latest assessment date within any visit) is considered as the EOS date.

For subjects prematurely discontinuing the study, reasons for premature discontinuation from study are: ‘Death’, ‘Lost to follow-up’, ‘Subject decision/Withdrawal of consent’ (further split into ‘Adverse event’, ‘Lack of efficacy’, ‘No reason provided’ and ‘Other’), ‘Physician decision’ (further split into ‘Adverse event’, ‘Lack of efficacy’ and ‘Other’) or ‘Sponsor decision’ (‘Other’). Whenever ‘Other’ is selected, free text can be provided in addition. An additional category ‘Reason not provided’ is defined for subjects where the reason is missing.

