5.4 Efficacy variables

5.4.1 Primary efficacy variable(s): ARR up to EOS

The primary endpoint is the Annualized Relapse Rate (ARR) up to EOS, based on confirmed relapses according to the treating neurologist / principal investigator. ARR is defined as the number of confirmed relapses per subject-year.

A confirmed relapse is defined as a record with 'Relapse meeting the criteria for a confirmed relapse?' answered 'Yes' on the 'Relapse Summary' eCRF. All confirmed relapses from randomization up to EOS will be included in the analysis.

For the statistical analysis of ARR, the following data will be used:

- Number of confirmed relapses from date of randomization up to EOS date;
- Length of observation expressed in years, defined as: [EOS date – date of randomization + 1] in days, divided by 365.25.

The logarithm of the length of observation up to EOS will be used as an offset variable in the primary efficacy and sensitivity analyses.

Confirmed relapses 'from date of randomization up to EOS date' includes all confirmed relapses unless starting prior to randomization.

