9.3 Display of subject disposition, protocol deviations and analysis sets

9.3.1 Subject disposition

The number and percent of subjects in the FAS is summarized by country and site.

A listing including subject disposition is also provided on the FAS.

Furthermore, a listing of study initiation and completion dates is also provided.

The number and percent of subjects screened and re-screened (incl. reasons for screening failure), subjects randomized, subjects completing study up to study termination, subjects treated, and subjects completing study treatment up to study termination, as well as subjects completing both treatment and study up to study termination are summarized for the SCR. For subjects that failed screening more than once, only the reason of the last failure is reported in the summary table.

All reasons for screening failures are included in the listing. The listing also includes the date of screening / re-screening, an indicator variable ('Yes', 'No') for failed screening attempts, the randomization date, and the number of days from successful screening to randomization.

The number and percent of subjects by reason for premature discontinuation from study is tabulated for the FAS. The number and percent of subjects by reason for premature discontinuation from study treatment is tabulated for the SAF. Listings of subjects with premature study/treatment withdrawal and related reasons are also provided on FAS.

A listing of randomization scheme and codes (for randomized subjects only) as well as a listing with Informed Consent information are produced respectively on FAs and SCR.

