9.6 Analysis of the primary efficacy variable

9.6.1 Hypothesis and statistical model

A generalized linear model with negative binomial distribution for the number of confirmed relapses will be assumed as described in Section 10.1.

Two-sided hypotheses are expressed in terms of the model parameters $\mu_{\text{Ponesimod}}$ and μ_{Placebo} . The primary null hypothesis is that the ARR (μ) does not differ between ponesimod and placebo. The alternative hypothesis is that the ARR differs between ponesimod and placebo.

$$\begin{aligned} H_{0, \text{ARR}}: \mu_{\text{Ponesimod}} - \mu_{\text{Placebo}} &= 0 \\ &\text{vs} \\ H_{1, \text{ARR}}: \mu_{\text{Ponesimod}} - \mu_{\text{Placebo}} &\neq 0 \end{aligned}$$

The null hypothesis will be tested by a two-sided Wald test within the negative binomial regression model [see Section 9.6.2], with a two-sided significance level of 0.05.

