9.6.2 Main analysis

The primary statistical analysis will be performed up to EOS on the FAS using a negative binomial (NB) regression model for confirmed relapses, with treatment as a factor and the binary stratification variable for EDSS category ($\text{EDSS} \leq 3.5$ versus $\text{EDSS} > 3.5$) from IRT included in the model. The model also includes an offset variable defined as the log of time on study (in years) from randomization up to EOS. The effect size will be measured by the relative reduction in the model estimated mean ARR for ponesimod compared to placebo including two-sided 95% Wald confidence interval (CIs).

Mean model-based estimates of the ARR (for confirmed relapses), by treatment arm, as well as 95% CIs are presented. A rate ratio comparing ponesimod 20 mg with placebo will be derived from the model including 95% CIs and the corresponding p-value. The dispersion parameter will also be displayed.

Descriptive summary statistics of the number of confirmed relapses as a continuous variable and the number of confirmed relapses in categories (0, 1, 2, 3, 4, ≥ 5), by treatment arm will be presented. The total cumulative number of confirmed relapses, as well as the total cumulative time on study (summed for all subjects) will also be displayed. From the total number of confirmed relapses and the total time on study the raw unadjusted ARR, by treatment arm, will be calculated and summarized.

The fit of the model will be assessed and other distributions such as the Poisson distribution will be considered in case of a lack of fit.

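### The FAS requires a post-baseline efficacy assessment that the relapse endpoints do not need, which can exclude only treated subjects without a confirmed relapse and leaves gaps in the study-discontinuation outputs

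*SAP*

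**What the plan says.** Section 7.1.2 of the SAP admits to the FAS "all randomized subjects who were treated with at least one dose of study treatment and have at least one post-baseline efficacy assessment". It does not say what counts as an efficacy assessment. Section 9.6.2 places the primary analysis on this set: "The primary statistical analysis will be performed up to EOS on the FAS using a negative binomial (NB) regression model for confirmed relapses". Section 9.6.1 specifies a Wald test "with a two-sided significance level of 0.05", and section 9.6.3 plans no sensitivity analysis.

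Section 5.4.1 builds the endpoint from two items: "Number of confirmed relapses from date of randomization up to EOS date" and "Length of observation expressed in years, defined as: [EOS date – date of randomization + 1] in days, divided by 365.25". If no EOS date is recorded, section 5.1.6 supplies one: "If missing, the last recorded visit date (i.e., the latest assessment date within any visit) is considered as the EOS date". Time to first confirmed relapse (section 5.4.2.2) uses the same relapse records and is censored at EOS.

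On disposition, section 9.3.1 states: "The number and percent of subjects by reason for premature discontinuation from study is tabulated for the FAS". It also puts the listings of study and treatment withdrawals and the listing of randomization codes on the FAS. Reasons for stopping study treatment are tabulated on the safety set (SAF), which needs only one dose.

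**The concern.** Membership of the primary analysis set depends on something that happens after randomization and is linked to the outcome. A relapse prompts a visit with an EDSS, which brings the subject into the FAS. A subject who leaves equally early, without a relapse and without any efficacy visit, is left out together with their relapse-free time. The endpoint gives no reason for this, because both of its ingredients exist for that subject.

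Two things are at stake. The first is a one-directional exclusion from the only confirmatory test left in the plan. The second is incomplete accounting: in a terminated trial with 136 randomized subjects, the table explaining why people left the study would omit some of the earliest leavers.

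**Working it through.** The SAP gives no relapse-rate, dropout or power figure to reproduce, so the check is to trace the rules and then illustrate their size.

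**Who can be excluded**

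1. Section 5.4.1.1 records whether a relapse qualifies as confirmed only for relapses with a completed EDSS. Every treated subject with a confirmed relapse therefore has an efficacy assessment and is in the FAS.
2. The assessment condition can therefore remove only treated subjects with zero confirmed relapses, and their observation time.
3. Routine EDSS is every 12 weeks (section 5.4.2.1). Table 3 also schedules EDSS and MRI at EOT, including a premature EOT, and EDSS at FU. Unscheduled visits may include either. An excluded subject must have missed all of these. The SAP foresees a missed EOT visit after premature discontinuation as an important deviation (Attachment 1, section 3.2).

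**Size on crude ARR**

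The assumptions, none from the SAP, are:
- true ARR λ of 0.2 to 0.5;
- a fraction d of 3–10% leaving before Week 12, after t = 42/365.25 = 0.115 years on average;
- a share v of 0–80% of these leavers having an efficacy visit anyway;
- T = 1 year of follow-up for everyone else.

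The probability of no relapse before leaving is p0 = exp(−λt). The inflation factor is

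[(1−d)T + dt] / [(1−d)T + dt − d(1−v)·p0·t].

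- λ = 0.35, d = 0.05, v = 0: p0 = 0.961, and 0.95575 / (0.95575 − 0.00552) = 1.0058, or +0.58%.
- λ = 0.2, d = 0.10, v = 0 (the largest case): 0.9115 / (0.9115 − 0.0112) = 1.0125, or +1.25%.
- d = 0.03, v = 0.8 (the smallest case): +0.07%.

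The number omitted, 136·d·(1−v)·p0 at λ = 0.35, runs from 0.8 to 13.1 subjects. As a simpler yardstick, five such subjects with up to 84 days each (assumed) remove at most 5 × 84/365.25 = 1.15 subject-years and no confirmed relapses. They are 5/136 = 3.7% of those randomized.

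**Size on the rate ratio**

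Take true rates of 0.25 and 0.35 (ratio 0.714). Equal early dropout of 5% leaves the ratio at 0.714. With 10% early dropout on ponesimod and 2% on placebo and v = 0, the arm factors are 1.0124 and 1.0023, giving 0.714 × 1.0124/1.0023 = 0.722. With 15% versus 2% the ratio is 0.727, a change of 1.7%. With v = 0.5 the two unequal cases give 0.718 and 0.720.

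**Type I error**

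A negative binomial simulation used 68 subjects per arm, equal true ARR of 0.35, dispersion fixed at 0.5, early leavers observed for 3–84 days and the others for 84–900 days, with 1,500 runs per scenario. The FAS rule gave rejection rates of 0.041 to 0.049. Including all treated subjects gave 0.043 to 0.047. The Monte Carlo standard error is √(0.05 × 0.95/1500) = 0.006.

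**Disposition**

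The study-discontinuation reasons need FAS membership, while the treatment-discontinuation reasons need one dose. The two tables therefore have different denominators. Neither covers subjects who were randomized and never dosed, a group with its own deviation code in Attachment 1, section 2.7.

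**The case against.** The strongest reply is that few subjects can be affected. An early leaver is due at EOT and at FU, and either visit gives entry without a relapse. After the decision to terminate, subjects on treatment were required to make both (section 2). If 50% or 80% of early leavers have such a visit, about 51–53% or 81% of them enter the FAS, mostly without a relapse. A reader might infer that early dropouts enter only through a relapse visit. The visit schedule does not support that. It holds only for those who miss EOT and FU, and even they could enter through another unscheduled efficacy assessment.

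The undefined term also matters. Subjects are reminded about new neurological symptoms at every visit, and section 11.4 lists Week 2 among the efficacy summary visits. A broad reading of efficacy assessment would admit nearly every treated subject. This reduces the likely harm, but it leaves membership of the primary set to interpretation.

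A reader might also take "In order to preserve the randomization, subjects will be evaluated according to the treatment they have been randomized to" as a claim that the set keeps everyone randomized. In context it explains analysis by assigned arm and stratum, so it is not a false statement.

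Finally, the omitted subjects do not vanish. The summary on the screened set counts those randomized, treated and completing the study. Set membership is listed (section 9.3.3), and all deviations are listed on the screened set (section 9.3.2). The numbers can be recovered. The tabulated reasons for leaving the study cannot.

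**Conclusion.** The point holds in a limited form. The post-baseline assessment condition serves no purpose for ARR or time to first confirmed relapse. Where it acts, it removes only treated subjects without a confirmed relapse, so it can only raise an arm's crude ARR. Under the assumed dropout the rise is about 1% or less in most scenarios. The shift in the rate ratio is at most about 2%, and only with strongly unequal early dropout between arms. The simulation showed no inflation of the type I error. These sizes rest entirely on assumed relapse rates, dropout and visit attendance, because the SAP does not say how many such subjects exist. The documents do not support a claim of material bias in the treatment effect.

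The accounting gap does not depend on those assumptions. As written, the study-discontinuation reasons, the withdrawal listings and the randomization listing omit every randomized subject outside the FAS.

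**What to change.** Analyse ARR and time to first confirmed relapse on all randomized subjects, in the arm and stratum assigned, with time from randomization to EOS. At minimum, drop the post-baseline assessment condition so that all treated subjects are included. Let the EDSS and MRI analyses use the subjects who have the data they need. Section 5.4.2.1 already has a censoring rule for subjects without a post-baseline EDSS. Present the study-discontinuation reasons, the withdrawal listings and the randomization listing on all randomized subjects.

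The cost is a change of SAP wording in sections 7.1.2, 7.2, 9.3.1, 9.6.2 and 9.7.2 and a few added records, best made before unblinding. The added subjects have short follow-up and carry little information. The day added in the observation-time formula keeps the log offset defined even for a subject who leaves on the day of randomization.

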7.1.3 Safety analysis set

The safety analysis set (SAF) includes all subjects who received at least one dose of study treatment. Irrespective of the randomized treatment group, subjects are summarized grouped:

- by actual treatment received, if the same kind of study treatment (ponesimod or placebo) was taken throughout the study.
- within the treatment group they were exposed to for the majority of time on study treatment in case both study treatments (ponesimod and placebo) were taken by a subject at some point

during the study. If a subject received ponesimod and placebo for exactly the same number of days, they are summarized within the treatment they are assigned to by randomization.

Some analyses are conducted based on the following safety set subsets:

- Subset of subjects with at least one re-initiation (based on eCRF Study Drug Administration - Re-Initiation).

7.1.4 Other analysis sets

The following other analysis sets are defined:

7.1.4.1 Post-treatment safety analysis set

Includes all subjects in the safety analysis set who have an EOS date > EOT + 15 days. Subjects are summarized in the same treatment group as in the safety analysis set.

7.1.4.2 Lymphocyte T cell subset analysis set

Includes all subjects in the safety analysis set who have at least one evaluable baseline and at least one evaluable post-baseline on-treatment sample for the lymphocyte T cell subset analysis.

7.1.4.3 Lymphocyte B cell subset analysis set

Includes all subjects in the safety analysis set who have at least one evaluable baseline and at least one evaluable post-baseline on-treatment sample for the lymphocyte B cell subset analysis.

7.2 Usage of the analysis sets

Table 5 provides an overview of the analysis set usage for the main variables of the study.

Table 5 Overview of the different main analysis sets and their usage

Analyses/Data Displays	Screened analysis set	Full analysis set	Safety analysis set
Inclusion/exclusion criteria	✓		
Demographic characteristics		✓	
Baseline characteristics		✓	
Previous and concomitant medications		✓	
Treatment exposure			✓
Efficacy: Primary endpoint		✓	
Efficacy: Secondary endpoints		✓	
Efficacy: Exploratory endpoints		✓	
Safety endpoints			✓
All subject listings		✓	

Main analysis of the primary efficacy endpoint is based on the Full analysis set, selected listings will be prepared on the Screened analysis set.

8 DEFINITION OF SUBGROUPS

Due to the low number of subjects recruited in this early terminated study, no subgroup analyses will be performed.

9 STATISTICAL ANALYSES

9.1 Overall testing strategy

9.1.1 Overall testing strategy

The primary endpoint (ARR using confirmed relapses) will be tested using a negative binomial regression model, comparing ponesimod with placebo. Due to the early termination of the study, analysis of the five secondary endpoints will be considered exploratory. No adjustment for multiplicity will be performed.

9.2 General rules for data presentations

This section describes the general rules applied for all data displays, unless otherwise specified in each corresponding section. Standard Guiding Rules and Principles and standard outputs are followed where applicable.

SAS version 9.4 is used for the preparation of all tables, listings and figures. Listings are sorted by treatment group, subject number (includes sorting by country and center) and timing (dates and/or visits as applicable). For analyses performed on multiple analysis sets, only one listing containing all analyzed subjects is presented. Names of outputs have a suffix that indicates the analysis set (e.g., _S for Safety set).

Data are listed and summarized using appropriate descriptive statistics:

- Number of non-missing observations, number of missing observations, mean, standard deviation, minimum, Q1, median, Q3, and maximum for continuous variables;
- Number of non-missing observations, and frequency with percentage per category (percentages based on the number of non-missing observations) for categorical endpoints;
- Some continuous variables are graphically presented based on mean change \pm standard error (SE) on a time axis scaled to the target days of the corresponding visit. The SE is derived as standard deviation $(SD)/\sqrt{N}$.
- All safety data will be included in listings, with flags for safety data considered to be treatment-emergent.

Example table layouts:

ACT-128800/JNJ-67896153
Analysis set: <Set>

Protocol: AC-058B302<TITLE>

	Ponesimod 20 mg / DMF N = XX	Placebo / DMF N = XX	Total N = xx
<XXX>	XX	XX	XX

Treatment groups are displayed in the order (left to right) of Ponesimod 20 mg / DMF, Placebo / DMF, Total (if applicable). For figures, ponesimod / DMF is displayed in red with solid line style and placebo / DMF is displayed in black with dashed line style.

9.3 Display of subject disposition, protocol deviations and analysis sets

9.3.1 Subject disposition

The number and percent of subjects in the FAS is summarized by country and site.

A listing including subject disposition is also provided on the FAS.

Furthermore, a listing of study initiation and completion dates is also provided.

The number and percent of subjects screened and re-screened (incl. reasons for screening failure), subjects randomized, subjects completing study up to study termination, subjects treated, and subjects completing study treatment up to study termination, as well as subjects completing both treatment and study up to study termination are summarized for the SCR. For subjects that failed screening more than once, only the reason of the last failure is reported in the summary table.

All reasons for screening failures are included in the listing. The listing also includes the date of screening / re-screening, an indicator variable ('Yes', 'No') for failed screening attempts, the randomization date, and the number of days from successful screening to randomization.

The number and percent of subjects by reason for premature discontinuation from study is tabulated for the FAS. The number and percent of subjects by reason for premature discontinuation from study treatment is tabulated for the SAF. Listings of subjects with premature study/treatment withdrawal and related reasons are also provided on FAS.

A listing of randomization scheme and codes (for randomized subjects only) as well as a listing with Informed Consent information are produced respectively on FAs and SCR.

